### **Statistical Analysis Plan (SAP)**

Baseline characteristics of participants were compared according to adherence to the Mediterranean diet. Means (SD) or percentages for each variable were calculated and the statistical significance of the differences will be assessed by one-way ANOVA and chi-squared tests.

All data will be assessed and compared using 95% confidence intervals (CI). Pearson

correlation coefficients (r) between each parameter will be assessed. If the Pearson coefficient is sensitive to data distribution, Spearman rank correlations can also be accounted.

Multivariable linear regression modelling can be used to compare adjusted differences between the different parameters. Finally, multivariable logistic regression will be used to estimate the association between the clinical and anthropometric parameters. A p value <0.05 will be considered as statistically significant.

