## **Objectives**

The main objective of this study is to evaluate the impact of ingestion of polyphenol-rich olive oil on important clinical parameters, such as anthropometric measurements, blood and urinary biomarkers, gene expression, and gut microbiota composition. To achieve this objective, a quasi-experimental clinical study will be conducted with the following tasks:

- 1) Recruitment of participants;
- 2) Intervention;
- 3) Periodic evaluation of the impact of olive oil ingestion on clinical parameters of participants, through:
  - 3.1) Administration of questionnaires;
  - 3.2) Anthropometric measurements;
  - 3.3) Analysis of blood biomarkers;
  - 3.4) Analysis of urinary biomarkers;
  - 3.5) Analysis of gene expression;
  - 3.6) Analysis of gut microbiota.

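### The SAP specifies no contrast between visits and no pairing of a participant's records, so change over the intervention has no pre-specified estimate

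*Combined protocol and SAP*

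**What the plan says.** The Objectives section states: "The main objective of this study is to evaluate the impact of ingestion of polyphenol-rich olive oil on important clinical parameters". One of the tasks listed under it is "Periodic evaluation of the impact of olive oil ingestion on clinical parameters of participants". Task 2 and Task 3 place the assessments at day 1, between days 40 and 50, and at day 90. Task 2 describes one group, which takes the oil daily for 3 months.

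The SAP is one short section. It contains:

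- **Baseline comparison.** "Baseline characteristics of participants were compared according to adherence to the Mediterranean diet", where "the statistical significance of the differences will be assessed by one-way ANOVA and chi-squared tests".
- **General statement.** "All data will be assessed and compared using 95% confidence intervals (CI").
- **Correlations.** Pearson coefficients between parameters, with Spearman as an alternative.
- **Linear regression, optional.** "Multivariable linear regression modelling can be used to compare adjusted differences between the different parameters".
- **Logistic regression.** "multivariable logistic regression will be used to estimate the association between the clinical and anthropometric parameters".
- **Decision rule.** "A p value <0.05 will be considered as statistically significant".

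The SAP mentions no visit other than baseline. It does not mention change, pairing, repeated measures or a participant effect.

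**The concern.** With one described group, the design can show an effect only as change in the same people between visits. That is the one quantity the SAP does not define. Two analysts could both follow the SAP and report different contrasts (day 90 against day 1, midpoint against day 1, or day 90 against midpoint) with different standard errors, depending on whether they pair the records. The contrast could also be settled after the data are seen. Pairing cannot be taken as understood, because the only difference tests that the SAP names are tests for independent groups.

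**Working it through.** The documents state no sample size, power, effect size or SD, so there is no figure of the plan's to reproduce. The check is a reading of the SAP against the objective, followed by illustrations.

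**Step 1: does any SAP sentence define a change between visits?**

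| SAP element | What is compared or related | Visit contrast or pairing specified? |
|---|---|---|
| One-way ANOVA, chi-squared | Baseline characteristics by diet adherence | No; baseline only |
| 95% CI sentence | All data, comparison not defined | No |
| Pearson, Spearman | One parameter with another | No |
| Linear regression (optional) | Adjusted differences between parameters | No; covariates not listed |
| Logistic regression | Clinical with anthropometric parameters | No; covariates not listed |

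The protocol's task sections fix when measurements are taken, not how they are compared, so they do not fill the gap.

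**Step 2: what an unpaired comparison would cost.** This is an illustration with a normal approximation, equal SD σ at both visits, n participants and an assumed within-person correlation ρ.

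- Variance of the day 90 minus day 1 mean difference, paired: 2σ²(1−ρ)/n. Treated as independent groups: 2σ²/n.
- Ratio of standard errors: k = 1/√(1−ρ).
- True two-sided error at nominal 5%: 2[1−Φ(1.96k)].
- Power for an effect with 80% paired power (1.96 + 0.84 = 2.80 paired standard errors): Φ(2.80 − 1.96k).

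| Assumed ρ | k | True error | Power |
|---|---|---|---|
| 0.3 | 1.20 | 0.019 | 68% |
| 0.5 | 1.41 | 0.006 | 51% |
| 0.7 | 1.83 | 0.0004 | 22% |

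**Step 3: what pooling visits would cost, if it were done.** Suppose the three visits entered a correlation or regression between person-level variables as independent rows. The design effect is 1 + 2ρ, which is 1.6, 2.0 and 2.4 for the same ρ. The true error of a nominal 5% test is 2[1−Φ(1.96/√(1+2ρ))], or about 12%, 17% and 21%. The SAP does not say whether visits are pooled, so this is conditional.

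**Step 4: would any mixed model do as the remedy?** A random participant intercept alone assumes equal correlation between all pairs of visits. Suppose instead that the correlation decays: r between adjacent visits and r² between day 1 and day 90. In large samples the model then uses the average correlation (2r + r²)/3. Its standard error for day 90 minus day 1 is √{[1 − (2r + r²)/3]/(1 − r²)} times the true one.

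- r = 0.5: √(0.583/0.75) = 0.88; true error 2[1−Φ(1.96 × 0.88)] = about 8.4%.
- r = 0.9: √(0.13/0.19) = 0.83; true error about 10.5%.

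A paired analysis keeps 5%, so a random-intercept model is not an equivalent alternative to it.

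**The case against.** The strongest reply is that the 95% CI sentence covers all data, visits included, and that any statistician would pair the records of a before-after study. The first part may well be the intention. The sentence still does not say what is compared with what, so it pre-specifies nothing. The second part is an argument for writing the pairing down.

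A second reply is that the regressions might include visit. That stands to this extent: no covariates are listed, so visit is unspecified, not excluded. A reader might infer that the SAP's models are shown to lack a visit term, but the text does not support that.

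Other stronger inferences also go too far:

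- **A count of 60 open contrasts** (20 named outcomes before microbiota, times three pairs of visits). Only blood is expressly sampled at three timepoints. For urine and gene expression, three visits are inferred from the task list. BMI, CHOL/HDL and VAI are derived from other measurements.
- **A false-positive rate of 8% to 12%.** This arises if someone picks the best of two or three correctly paired contrasts. It describes selective reporting, which the plan does not prescribe, and does not measure the lack of pairing.
- **Invalid baseline tests.** They use one record per participant, so repeated measures do not affect them.
- **A hidden second group or period.** Task 2 speaks of an intervention group and of each intervention period, but the latter may mean only dispensing intervals. The text otherwise describes one group and one 90-day period.

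**Conclusion.** The point holds as an omission. Followed as written, the SAP pre-specifies no estimate of change over the intervention, although that change is the only effect measure the described design offers. This is more than missing detail, because the analyses that are named address other questions.

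Its size for this trial is unknown. The figures in Step 2 rest on assumed correlations of 0.3 to 0.7, equal SDs and an analyst who ignores pairing. The SAP leaves that open but does not prescribe it.

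A reader might also infer that naming the contrast would make the trial a test of the oil's effect. It would not. Without a control, the estimate is change over 90 days, and that limit belongs to the design.

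**What to change.** - For each outcome measured at both visits, make the main analysis the within-participant day 90 minus day 1 change with its 95% CI. Use either a paired analysis or a mixed model with visit as a categorical effect and an unstructured within-participant covariance, and state which. A random intercept alone is not enough (Step 4).
- Make midpoint minus day 1 secondary. The documents do not rank the visits, so the sponsor may prefer another order, but it should be fixed before results are seen.
- If correlations or regressions use more than one visit per participant, run them on within-person changes or account for clustering by participant.
- Report the estimate as change over 90 days without a control, not by itself as an effect of the oil.

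The cost is minor SAP wording and analysis work in standard software. No new data, visits or participants are needed.

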### Task 3.3 - Analysis of Blood Biomarkers

This task aims to assess the impact of olive oil consumption on various blood biomarkers through the analysis of capillary blood samples. Capillary blood will be collected from a finger of the hand using a single-use lancet at three timepoints during the intervention study. The capillary blood samples (volume in  $\mu\text{L}$ ) will be analyzed using the cobas® b101 device (Roche), a Point of Care equipment that allows for rapid quantitative measurement of glycated hemoglobin (HbA1c), estimated average glucose (eAG), triglycerides (TG), total cholesterol (CHOL), high-density lipoprotein cholesterol (HDL), low-density lipoprotein cholesterol (LDL), atherogenic index (CHOL/HDL), and C-reactive protein. These data will be used to calculate the visceral adiposity index (VAI) using the formulas described below:

- Male VAI : 
$$\left[ \frac{WC \text{ (cm)}}{\left\{ 39.68 + (1.88 \times BMI \left( \frac{\text{kg}}{\text{m}^2} \right)) \right\}} \right] \times \left[ \frac{TG(\text{mmol/l})}{1.03} \right] \times \left[ \frac{1.31}{HDL(\text{mmol/l})} \right]$$
- Female VAI : 
$$\left[ \frac{WC \text{ (cm)}}{\left\{ 36.58 + (1.89 \times BMI \left( \frac{\text{kg}}{\text{m}^2} \right)) \right\}} \right] \times \left[ \frac{TG(\text{mmol/l})}{0.81} \right] \times \left[ \frac{1.52}{HDL(\text{mmol/l})} \right]$$

VAI: Visceral Adipose Index, WC: Waist Circumference, BMI: Body Mass Index, TG: Triglyceride, HDL: High Density Lipoprotein

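### The SAP commits to logistic regression for clinical–anthropometric associations, although the measures are all quantities with no cut-off (minor; cheap to improve)

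*Combined protocol and SAP*

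**What the plan says.** The Statistical Analysis Plan (SAP) names three tools for relating one measurement to another.

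- **Correlation, firm:** Pearson "correlation coefficients (r) between each parameter will be assessed". A rank version is allowed: "If the Pearson coefficient is sensitive to data distribution, Spearman rank correlations can also be accounted".
- **Linear regression, optional:** "Multivariable linear regression modelling can be used to compare adjusted differences between the different parameters".
- **Logistic regression, firm and listed last:** "multivariable logistic regression will be used to estimate the association between the clinical and anthropometric parameters".

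A general rule closes the section: "A p value <0.05 will be considered as statistically significant". The SAP names no dependent variable, event, cut-off or covariate for the logistic model.

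The measures are defined in the protocol:

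- Task 3.2 gives height, weight, waist circumference (WC), fat mass, lean mass, BMI (weight over height squared), and systolic and diastolic blood pressure.
- Task 3.3 gives HbA1c, estimated average glucose, triglycerides (TG), total cholesterol (CHOL), HDL, LDL, and then "atherogenic index (CHOL/HDL), and C-reactive protein". It adds: "These data will be used to calculate the visceral adiposity index (VAI) using the formulas described below". Those formulas use WC, BMI, TG and HDL.
- Task 3.4 gives urinary 8OHdG normalised to creatinine.

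**The concern.** Binary logistic regression needs a two-category outcome, and none of the measures in Tasks 3.2 to 3.4 is one. To carry out the sentence as written, the analyst must first turn a quantity into two groups at a point the plan does not give. That has two consequences. Precision is lost, because values on the same side of the cut are treated as equal. The result also depends on a choice that can be made after the data are seen. Linear regression needs no cut, but the SAP only permits it, and for a differently worded purpose (adjusted differences).

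There is a smaller issue in the same section. Correlations between all parameters include an index and the quantities it is calculated from. Part of such a correlation is arithmetic, and the SAP does not set these pairs apart.

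**Working it through.** **Type of each measure.** Task 3.2 defines 8 quantities, Task 3.3 defines 9 (counting VAI) and Task 3.4 defines 1, so 8 + 9 + 1 = 18. None is binary and none has a cut-off. The percentages and chi-squared tests in the SAP concern baseline characteristics by Mediterranean diet adherence and supply no cut-off either.

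**Information kept after a cut.** The plan has no figure to reproduce: it states no sample size, power or cut-off. The splits below are assumptions. For a normal outcome cut so that a fraction p lies on one side, and a weak association, the information kept relative to linear regression is φ(z_p)² / [p(1 − p)], where φ is the standard normal density and z_p the p-quantile.

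| Split | φ(z_p) | Information kept | N needed for equal precision |
|---|---|---|---|
| 50/50 | 0.399 | 0.399² / 0.25 = 0.64 | 1/0.637 = 1.57 times |
| 20/80 | 0.280 | 0.280² / 0.16 = 0.49 | 1/0.490 = 2.04 times |
| 10/90 | 0.175 | 0.1755² / 0.09 = 0.34 | 1/0.342 = 2.92 times |

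**In terms of power.** If linear regression has 80% power at two-sided 0.05, its standardised effect is 1.96 + 0.84 = 2.80. Multiplying by the square root of the information kept gives:

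- 50/50: 2.80 × √0.637 = 2.24, so power is Φ(2.24 − 1.96), about 61%.
- 20/80: 2.80 × √0.490 = 1.96, so power is about 50%.
- 10/90: 2.80 × √0.342 = 1.64, so power is Φ(1.64 − 1.96), about 37%.

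This large-sample result does not depend on N. Simulation with one predictor agrees: 62%, 50% and 36% at n = 30 (true r 0.485), and 61%, 50% and 37% at n = 100 (true r 0.276).

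**Formula-linked correlations.** Eight pairs are linked directly: VAI with WC, BMI, TG and HDL; CHOL/HDL with CHOL and HDL; BMI with weight and height. Three are linked indirectly: VAI with weight and with height (through BMI), and VAI with CHOL/HDL (through HDL). The arithmetic part was simulated with lognormal inputs. The assumed coefficients of variation (CVs) were weight 15%, height 5%, CHOL 18%, HDL 20–30%, TG 25–60% and WC 10–15%. The documents give no CVs and no correlations between inputs.

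*Strong and stable:*

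- BMI–weight is 0.83 with unrelated inputs, and at least 0.74 when weight and height correlate at 0.5–0.6.
- CHOL/HDL–HDL is −0.71 to −0.78 with unrelated inputs, and −0.59 or stronger when CHOL and HDL correlate at 0.4.
- VAI–TG is 0.56 to 0.93 with the WC–BMI correlation between 0 and 0.8. An inverse TG–HDL correlation strengthens it, since VAI rises with TG and falls with HDL.

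*Dependent on unstated input correlations:*

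- BMI–height is −0.55 at a weight–height correlation of 0, −0.36 at 0.3, −0.19 at 0.5 and −0.08 at 0.6. On the log scale the covariance is ρ·s_w·s_h − 2·s_h², which is zero at ρ = 2·s_h/s_w, about 2 × 5/15 = 0.67. The share of samples of 30 with p<0.05 falls from 91% at correlation 0 to 7–8% at 0.6.
- CHOL/HDL–CHOL with HDL CV 30% is 0.51 at a CHOL–HDL correlation of 0, 0.22 at 0.4 and 0.01 at 0.6. The zero point is ρ = s_CHOL/s_HDL, about 18/30 = 0.60. The share with p<0.05 falls from 84% to 5%. With HDL CV 20% the correlation is still 0.35 at ρ = 0.6.

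*Dependent on the assumed CVs:* VAI–HDL is −0.28 to −0.68, and VAI–CHOL/HDL is 0.22 to 0.63.

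*No general excess:* VAI with WC, BMI, weight and height. At a WC–BMI correlation of 0.8, p<0.05 occurs in 5–21% of samples of 30 for VAI–WC and in 5–7% for VAI–BMI. Over WC–BMI correlations of 0.6–0.8 the range is 5–8% for VAI–weight and VAI–height.

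**The case against.** The strongest reply is that the SAP does examine these relationships without a cut. Correlations are firmly planned and cover every pair on the continuous scale, linear regression is available, and the logistic model comes last. This stands as a limit on the harm. It does not remove the point: the correlations are unadjusted, and linear regression is neither promised nor assigned to this purpose.

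A second reply is that the loss figures rest on invented splits and a single predictor, while the planned model is multivariable. That is fair. They show how the cost varies with the cut and are not estimates for this trial. Accepted clinical cut-offs may also exist for some measures, but the plan adopts none, so the choice stays open.

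A third is that Objectives counts gene expression and gut microbiota among the clinical parameters. Those measures, and the questionnaire variables, are outside this point, which concerns Tasks 3.2 to 3.4.

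On the correlations, a matrix that includes BMI with weight is ordinary description, and the formulas are in the protocol. The SAP says correlations will be assessed; that each will be tested is only an inference from its general p-value rule. This is why the correlation point is subsidiary.

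**Conclusion.** A minor point and a cheap improvement. The only adjusted model firmly committed for clinical–anthropometric associations needs an undefined cut. That cut would keep about 64%, 49% or 34% of the information at 50/50, 20/80 or 10/90, assuming a normal outcome and a weak association. The mismatch between method and measures rests on the text alone; only its size rests on assumptions.

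A reader might infer three stronger things that the documents do not support:

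- *That the estimate of the oil's effect is weakened.* The sentence concerns associations between measurements, which is a secondary analysis.
- *That these associations are never analysed as continuous.* The correlations do that, without adjustment.
- *That formula-linked correlations will generally be significant by arithmetic.* A strong link held up for BMI–weight, CHOL/HDL–HDL and VAI–TG as input correlations were varied. For BMI–height and CHOL/HDL–CHOL it can vanish at plausible values of correlations that the documents do not give. For VAI–HDL and VAI–CHOL/HDL its size varies with the assumed CVs, and for the four VAI–anthropometric pairs no general excess is claimed.

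Whatever its size, a correlation between an index and its own input is not evidence of a separate biological association.

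**What to change.** Replace the logistic sentence in the SAP with:

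*Associations between clinical and anthropometric parameters will be estimated by multivariable linear regression of the continuous clinical parameter (log scale where skewed), with a participant random intercept if more than one visit is used; VAI is not regressed on its own inputs. Any logistic regression is supplementary and uses cut-offs fixed before analysis.*

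Add to the correlation paragraph:

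*Correlations of an index with its own inputs (VAI with WC, BMI, TG and HDL; CHOL/HDL with CHOL and HDL; BMI with weight and height) are flagged as formula-linked and are not interpreted as separate associations.*

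The cost is SAP wording only, using data already planned. The downside is that odds ratios against cut-offs are no longer the main result of this secondary analysis.

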### Task 2 - Intervention

Participants will include in their usual diet the daily intake of 30 mL of polyphenol-rich olive oil (intervention group) for 3 months. At the beginning (day 1), midpoint (between days 40 and 50), and end of the intervention period (day 90), participants will be assessed. The olive oil will be placed in dark-colored containers to minimize loss of phenolic content due to sunlight. The containers with the olive oil will be provided free of charge to participants at the beginning of each intervention period. Participants' adherence to olive oil intake will be verified through two processes: 1) by returning the containers at the end of each intervention period for the measurement and recording of the daily amount of unconsumed olive oil; 2) by quantifying hydroxytyrosol by GC-MS or LC-MS in 24-hour urine samples collected from participants who agree to this urine collection.

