#### Task 3.2 - Anthropometric Measurements

Anthropometric measurements, obtained according to standardized protocols, include the measurement of height, body weight, waist circumference (WC), and collection of body composition data. Height and weight will be measured with a stadiometer and a scale, respectively, with participants barefoot. Waist circumference will be measured at the midpoint between the last rib and the iliac crest using a flexible measuring tape. Body composition data, including fat mass and lean body mass, will be collected through

bioelectrical impedance analysis (BIA). Body mass index (BMI) will also be calculated by dividing weight by height squared. In addition to anthropometric measurements systolic and diastolic blood pressure will be measured using a sphygmomanometer after the participant has rested for 5 minutes.

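### The SAP sets one unadjusted p<0.05 rule over at least 20 outcomes, with no primary outcome, primary contrast, multiplicity procedure or exploratory label

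*Combined protocol and SAP*

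**What the plan says.** The decision rule is the last sentence of the SAP: "A p value <0.05 will be considered as statistically significant". It follows ANOVA and chi-squared tests, correlations, and linear and logistic regressions, and it is not tied to any one of them.

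The analyses the SAP names are:
- Comparisons at baseline, with an explicit assessment of statistical significance: "Baseline characteristics of participants were compared according to adherence to the Mediterranean diet".
- Associations among all measures: "correlation coefficients (r) between each parameter will be assessed", with rank correlations as an alternative.
- Optional linear regression, and logistic regression for associations between clinical and anthropometric parameters.
- A general statement that data will be compared using 95% confidence intervals.

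The SAP names no test of change over time. Under Objectives, the main aim covers whole domains: "important clinical parameters, such as anthropometric measurements, blood and urinary biomarkers, gene expression, and gut microbiota composition". Task 2 sets three assessments: "At the beginning (day 1), midpoint (between days 40 and 50), and end of the intervention period (day 90), participants will be assessed". Future Perspectives expects to establish whether the oil alters serum biomarkers, blood pressure, anthropometry and the microbiota, and to take the results to healthcare professionals and the general public.

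**The concern.** A threshold of 0.05 limits the false positive risk to 5% for one test chosen in advance. Here neither the outcome nor the contrast is chosen in advance. With many outcomes, two post-baseline visits and several kinds of analysis, the analyst can pick the results that fall below 0.05 after seeing the data and still follow the SAP as written. The stated rule then says little about how often such a result would appear if the oil did nothing.

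This matters because the intended message is about effect, and the planned audience includes clinicians giving nutritional advice and the mainstream media. A reader of the report could not tell a pre-planned result from a selected one.

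**Working it through.** The documents state no family-wise error rate, sample size or power, so there is no figure of the plan's own to reproduce.

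**Step 1. Count the named outcomes.**
- Task 3.2: weight, BMI, waist circumference, fat mass, lean mass, systolic and diastolic blood pressure = 7.
- Task 3.3: HbA1c, eAG, TG, CHOL, HDL, LDL, CHOL/HDL, C-reactive protein = 8, plus VAI = 1.
- Task 3.4: creatinine-normalised 8OHdG = 1.
- Task 3.5: SOD1, CCL2, NFkB = 3.
- Total: 7 + 8 + 1 + 1 + 3 = 20.

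Height (taken as fixed in adults), urinary creatinine (used only to normalise) and urinary hydroxytyrosol (an adherence check) are left out. Twenty is a minimum: the gene list in Task 3.5 is given as examples, and Task 3.6 adds bacterial populations, short-chain fatty acids, lactic acid and metabolites.

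**Step 2. Expected false positives (illustration).** Assume one test per outcome at 0.05 and no true change in any. The expected number is m × α = 20 × 0.05 = 1.0. Expectations add regardless of dependence, so correlation does not alter this. Testing both post-baseline visits gives 40 × 0.05 = 2.0.

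**Step 3. Chance of at least one.** If the tests are independent, 1 − 0.95^20 = 0.642, or 64%. Three outcomes are computed from others on the list: BMI ("Body mass index (BMI) will also be calculated by dividing weight by height squared"), CHOL/HDL and VAI. Without them, 1 − 0.95^17 = 0.582, or 58%, again under independence. Correlation lowers these figures, but the documents give no correlations, so the true value cannot be computed. To show the direction only, an assumed common correlation of 0.3, 0.6 or 0.9 among the 20 test statistics gives about 54%, 35% or 15% by simulation.

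**Step 4. The correlations the SAP does name.** Among 20 outcomes at one visit there are 20 × 19 / 2 = 190 pairs. Each truly unrelated pair adds 0.05 expected false positives. No total follows, because the number of unrelated pairs is unknown and some pairs are linked by construction.

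**The case against.** **The SAP does not plan 20 tests of change.** This is right. A reader might infer that 64% is the plan's own error rate, or that a false positive is certain. The documents support neither: one test per outcome is an illustration, and an expected count of 1.0 is not a certainty. The figure also needs every null to be true, and the Introduction presents lipid changes with olive oil as already shown. In general the expectation is 0.05 times the number of outcomes that truly do not change. What stands is the absence itself. With no contrast named, there is more freedom to choose afterwards, not less.

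**The study is exploratory in nature.** That may be the intention, and the planned 95% confidence intervals already suit it. But no section says so, and the 0.05 rule and the planned statements about impact point the other way. If exploration is intended, the label is the remedy.

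**Strict error control is a preference in a single-group study.** This is partly right. Holm testing after a gate is one design choice among several, so it is only an option below. Nor would it make a change attributable to the oil, since Task 2 describes only an intervention group.

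**The past tense in the SAP.** A reader might infer from the baseline sentence that outcome data had already been analysed. The text does not show this: the wording concerns baseline characteristics, and the rest of the SAP is mostly in the future tense. It justifies a question, not an allegation.

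**Conclusion.** The point holds as a gap in pre-specification. One unadjusted 0.05 rule is stated without limit of scope. No outcome, contrast, multiplicity procedure or exploratory label is fixed, while at least 20 outcomes are measured at three visits and conclusions about effect are expected. This rests on the text alone and is firm.

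The size is conditional. Under one test per outcome and no true change, the expected number of false positives is 1.0 for any correlation, and the chance of at least one is 64% under independence and lower under correlation. No more exact figure can be drawn from the documents. The conclusion that the error rate is not 5% does not depend on a particular value.

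**What to change.** Amend the SAP before outcome data are analysed:

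1. Name one primary outcome, chosen and justified by the sponsor, and one primary contrast (day 90 minus day 1), with a named paired or repeated-measures test at two-sided 0.05.
2. Label everything else exploratory: the other outcomes, midpoint contrasts, correlations, regressions, microbiota and metabolite measures, and the baseline comparisons by Mediterranean-diet adherence. Report these as estimates with the 95% confidence intervals the SAP already plans, and make no significance claim. The baseline comparisons need explicit mention because the SAP ties significance to them most directly.
3. Optionally, if confirmatory secondary claims are wanted, test a closed, listed set by Holm, only after a significant primary result. The length of that list sets the denominator, so the gene list must be closed if genes are included.
4. State whether outcome data had been examined when the SAP was written. If they had, label all results exploratory.

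**Cost.** This is wording only and needs no extra data. The exploratory route gives up significance claims on non-primary outcomes. The Holm route loses power. As an assumed example, with 18 secondaries the first step is 0.05/18 = 0.0028 (z = 2.991). An outcome with 80% power at 0.05 would then have Φ(1.960 + 0.842 − 2.991) = 42%, or 0.425 × 0.80 = 34% after gating on an independent primary with 80% power. Later Holm steps are milder. If the primary is not significant, no secondary claim can be made.

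None of this removes time-trend bias in a study without a described control group. That needs separate attention.
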